12.1.3. Severity Criteria

All AEs and laboratory data will be coded for severity using the toxicity grading table in [Attachment 1](#). *Note:* Laboratory values within local laboratory normal ranges (even if within a toxicity grade range), or laboratory values outside normal ranges that are not clinically significant in the judgment of the investigator, should not be recorded as AEs. For AEs not identified in the grading table, the following guidelines will be applied:

Mild (Grade 1): No interference with activity.

Moderate (Grade 2): Some interference with activity not requiring medical intervention.

Severe (Grade 3): Prevents daily activity and requires medical intervention.

Potentially life-threatening (Grade 4): Symptoms causing inability to perform basic self-care functions OR medical or operative intervention indicated to prevent permanent impairment, persistent disability.

The toxicity grading scale used for laboratory assessments is based on the FDA toxicity grading table, consistent with the assessment grading used throughout the protocol. If a laboratory value falls within the grading as specified in the FDA table, but also within the laboratory normal limits, the value is considered as normal. For hemoglobin, both the actual value and the change from reference will be graded.

The investigator should use clinical judgment in assessing the severity of events not directly experienced by the subject (eg, laboratory abnormalities).

The severity of solicited AEs will be graded in the diary by the subject based on the severity assessment provided in the diary and then verified by the investigator using the FDA toxicity grading table (see [Attachment 1](#)).

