Injection site swelling is a visible enlargement of an injected limb. It may be either soft (typically) or firm (less typical). Injection site induration is a palpable thickening, firmness, or hardening of soft tissue, usually has well-demarcated palpable borders, can be visible (raised or sunken compared to surrounding skin), is often 'woody' to touch and has a flat shape. As differentiation between swelling and induration may be difficult without health care professional's assessment, both symptoms have been combined to allow self-assessment by the subjects. Both swelling and induration can best be described by looking and measuring.

Note: any other injection site events not meeting the above case definitions should be reported separately as unsolicited AEs.^{20,21}

Systemic Adverse Events

Subjects will be instructed on how to record daily temperature using a thermometer provided for home use. Subjects should record body temperatures in the diary in the evening of the day of vaccination, and then daily for the next 7 days approximately at the same time each day.^a If more than one measurement is made on any given day, the highest temperature of that day will be used in the eCRF.

^a The 7-day post-vaccination temperature measurements may be taken earlier to coincide with the corresponding clinic visit.

Fever is defined as endogenous elevation of body temperature $\geq 38^{\circ}\text{C}$, as recorded in at least one measurement.²⁴

Subjects will also be instructed on how to note daily in the diary for 7 days after vaccination symptoms of the following events: fatigue, headache, myalgia, arthralgia, chills, nausea, and fever (ie, body temperature $\geq 38^{\circ}\text{C}$).

The severity of these solicited systemic AEs will be graded by the investigator according to the criteria presented in Section 12.1.3.

If a solicited local or systemic AE is not resolved by 7 days after vaccination, the follow-up will be captured on the diary. The subject will be instructed to record the date of last symptoms and maximum severity in the diary after resolution.

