11.10. Study Vaccination Pausing Rules

The investigator and the SRP will monitor the study vaccination pausing rules. If study vaccination is considered to raise significant safety concerns, further vaccination of subjects will be suspended until DRC review is carried out and subsequent communication between the sponsor and the investigators takes place.

The occurrence of any of the following events will lead to suspension of further study vaccination, and trigger a meeting of the DRC to discuss study suspension, adaptation or discontinuation of further vaccination:

1. One or more subject experience an SAE or other potentially life-threatening (Grade 4) event that is determined to be related to study vaccine; *OR*
2. One or more subjects experience anaphylaxis clearly not attributable to other causes than vaccination with study vaccine; *OR*
3. Two or more subjects experience a Grade 3 or 4 unsolicited AE of the same type, determined to be related to study vaccine, that persists for 72 hours or longer; *OR*
4. Two or more subjects experience a Grade 3 or 4 solicited systemic AE of the same type, determined to be related to study vaccine, that persists for 72 hours or longer; *OR*
5. Two or more subjects experience a persistent (upon repeat testing) Grade 3 or 4 laboratory abnormality related to the same laboratory parameter and considered related to study vaccine, that persists for 72 hours or longer; *OR*
6. Death of any subject, regardless of causality.

If any of the above specific pausing rules are met, the DRC will make recommendations regarding the continuation of the study to the sponsor. Study suspensions or terminations will occur within 5 working days after the decision is made, unless local regulations specify a shorter timeframe. Local regulatory authorities including IECs/IRBs will be informed within the appropriate regulatory-mandated timeframes. A study may be resumed only upon approval of a substantial amendment to the initial study application by the local regulatory authorities and IECs/IRBs. The sponsor will communicate conclusions regarding study continuation to the investigators, the IECs/IRBs and the national regulatory authorities as appropriate.

The investigator may ask for a review meeting to be held for any single event or combination of multiple events which, in his/her professional opinion, jeopardize the safety of the subjects or the reliability of the data.

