Nausea/vomiting	No interference with activity or 1 - 2 episodes/24 hours	Some interference with activity or >2 episodes/24 hours	Prevents daily activity, requires outpatient IV hydration	ER visit or hospitalization for hypotensive shock
Diarrhea	2 - 3 loose stools or <400 gms/24 hours	4 - 5 stools or 400 - 800 gms/24 hours	6 or more watery stools or >800gms/24 hours or requires outpatient IV hydration	ER visit or hospitalization
Headache	No interference with activity	Repeated use of non-narcotic pain reliever >24 hours or some interference with activity	Significant; any use of narcotic pain reliever or prevents daily activity	ER visit or hospitalization
Fatigue	No interference with activity	Some interference with activity	Significant; prevents daily activity	ER visit or hospitalization
Myalgia	No interference with activity	Some interference with activity	Significant; prevents daily activity	ER visit or hospitalization
Systemic Illness	Mild (Grade 1)	Moderate (Grade 2)	Severe (Grade 3)	Potentially Life-threatening (Grade 4)
Illness or clinical adverse event (as defined according to applicable regulations)	No interference with activity	Some interference with activity not requiring medical intervention	Prevents daily activity and requires medical intervention	ER visit or hospitalization

B: Tables for Laboratory Abnormalities

The grading scale used for laboratory assessments is based on the FDA Guidance document “Toxicity Grading Scale from Healthy Adult and Adolescent Volunteers Enrolled in Preventive Vaccine Clinical Trials”. Any laboratory value shown as a “graded” value in the table that is within the local laboratory normal ranges will not be graded for severity or recorded as AE. For hemoglobin, both the actual value and the change from reference will be graded. For the change from reference, the corresponding actual value should also be at least Grade 1.

Serum *	Mild (Grade 1)	Moderate (Grade 2)	Severe (Grade 3)	Potentially Life- threatening (Grade 4) **
Sodium – Hyponatremia - mEq/L	132 – 134	130 – 131	125 – 129	< 125
Sodium – Hypernatremia - mEq/L	144 – 145	146 – 147	148 – 150	> 150
Potassium – Hyperkalemia - mEq/L	5.1 – 5.2	5.3 – 5.4	5.5 – 5.6	> 5.6
Potassium – Hypokalemia - mEq/L	3.5 – 3.6	3.3 – 3.4	3.1 – 3.2	< 3.1
Glucose – Hypoglycemia - mg/dL	65 – 69	55 – 64	45 – 54	< 45
Glucose – Hyperglycemia Fasting - mg/dL	100 – 110	111 – 125	> 125	Insulin requirements or hyperosmolar coma
Random Glucose - mg/dL	110 – 125	126 – 200	>200	

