7.1. Adverse Events (AE)

7.1.1. Definitions

Solicited AEs, collected for 7 days after vaccination, shown in the tables are extracted from the diary pages of the CRF. For unsolicited AEs, only AEs with start date (grade and/or relation) within the 28-day period following vaccination or challenge will be presented in the safety tables except for SAE, which will be captured and tabulated in the outputs covering the whole study period. All other collected unsolicited adverse events will be presented through listings.

Solicited local AEs will be by definition considered as related to the study vaccine.

The severity of the AEs will be classified as grade 1 to 4. Solicited events that are graded less than grade 1, are not considered as AE. In case no grades are available, the grading of the solicited events will occur according to the grading list in [Attachment 1](#).

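### Arthralgia and chills have no named grading row, so loss of daily activity that is Grade 3 for fatigue, myalgia or headache may not be Grade 3 for them

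*Protocol*

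**What the plan says.** Protocol Section 9.2.6.1 lists the solicited systemic events: "fatigue, headache, myalgia, arthralgia, chills, nausea, and fever". It then says: "The severity of these solicited systemic AEs will be graded by the investigator according to the criteria presented in Section 12.1.3".

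Section 12.1.3 refers the reader to the table in Attachment 1 and adds a default: "For AEs not identified in the grading table, the following guidelines will be applied". On that default scale Grade 2 is "Some interference with activity not requiring medical intervention", and Grade 3 is given as "Severe (Grade 3): Prevents daily activity and requires medical intervention". The section also says that the subject grades solicited events in the diary first and the investigator then verifies the grade against Attachment 1.

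For both fatigue and myalgia, Attachment 1 defines Grade 3 as "Significant; prevents daily activity".

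Pausing rule 4 in Section 11.10 begins "Two or more subjects experience a Grade 3 or 4 solicited systemic AE of the same type". It also requires that the events be related to study vaccine and persist for at least 72 hours.

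SAP 7.1.1 takes solicited events from the diary pages. Where a grade is missing, it says that "the grading of the solicited events will occur according to the grading list in" SAP Attachment 1. SAP 7.1.2 tabulates solicited events by worst grade and separately at Grade 3.

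**The concern.** Solicited events are part of the secondary safety endpoint. A reader of the Grade 3 table will compare myalgia with arthralgia, and fatigue with chills, and will assume that Grade 3 means the same degree of impairment in each row. If two symptoms need an extra condition to reach Grade 3, their rates can look lower because of the definition and not because of the vaccine.

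The same grades feed pausing rule 4, and Section 11.9 plans no routine reviews by the Data Review Committee. Both symptoms are expected. Section 1.1 names chills among the most common solicited systemic events with the earlier Ad26 RSV vaccine, and Section 1.3.4 lists chills and joint pain after Ad26-vectored vaccines.

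**Working it through.** The plan gives no figure on this point, so there is none to reproduce. The check is a comparison of texts, followed by an illustration on assumed rates.

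**Step 1: match the solicited list to the rows of protocol Attachment 1.** Nausea, headache, fatigue and myalgia have rows in the systemic table, and fever has one under vital signs. Arthralgia and chills have no named row. That is 5 of 7 named and 2 of 7 not.

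**Step 2: find where the two unnamed symptoms go.** There are two routes: the Section 12.1.3 default, or the general illness row at the end of the systemic table in Attachment 1. The Grade 3 wording is the same on both.

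**Step 3: grade one event on each scale.** Take an event that prevents daily activity but does not require medical intervention.

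| Symptom | What Grade 3 needs | Grade of this event |
|---|---|---|
| Fatigue, myalgia | Loss of daily activity | 3 |
| Headache | Loss of daily activity, or any narcotic analgesic | 3 |
| Nausea | Loss of daily activity, with outpatient intravenous hydration | Not clearly 3 |
| Arthralgia, chills | Loss of daily activity and required medical intervention | Not 3; exceeds the Grade 2 wording |

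Grade 2 on the default scale covers only partial interference, so the arthralgia or chills event falls between Grades 2 and 3.

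**Step 4: check Grade 4.** Section 12.1.3 includes inability to perform basic self-care. The fatigue, myalgia and headache rows need an emergency room visit or hospitalization, as does the general illness row. At the top of the scale, the Section 12.1.3 route could therefore grade arthralgia or chills higher than the named symptoms.

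**Step 5: check the SAP fallback.** SAP Attachment 1 as shown contains blood and urine tables only. It cannot grade any solicited symptom.

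**Step 6: illustrate the effect on the two-subject count in rule 4.** All rates here are assumptions. Let p be the share of active-arm subjects with related chills (or arthralgia) that prevents daily activity for 72 hours or longer, and q the share of those who require medical intervention. With independent subjects, P(2 or more) = 1 − (1 − r)^n − n·r·(1 − r)^(n−1). Here r = p on the fatigue/myalgia wording and r = p·q on the default Grade 3 wording.

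Example with n = 22, p = 0.10, q = 0.25:
- r = 0.10: 1 − 0.0985 − 0.2407 = 0.661
- r = 0.025: 1 − 0.5729 − 0.3232 = 0.104

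| n active | p | Fatigue/myalgia wording | Default, q = 10% | q = 25% | q = 50% |
|---|---|---|---|---|---|
| 22 | 5% | 0.302 | 0.005 | 0.031 | 0.104 |
| 22 | 10% | 0.661 | 0.020 | 0.104 | 0.302 |
| 22 | 20% | 0.952 | 0.071 | 0.302 | 0.661 |
| 35 | 10% | 0.878 | 0.048 | 0.218 | 0.528 |

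The n = 35 row is the active half of the maximum of 70 vaccinated. The default columns ignore Grade 4. Any event that reaches Grade 4 through loss of self-care would raise them.

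**The case against.** **The wording is deliberate.** Amendment 2 aligned the Section 12.1.3 criteria with the FDA severity criteria for events not in the tables. That explains the text. It does not address two solicited symptoms falling into a scale meant for unlisted events.

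**A table route exists.** A reader might infer that these symptoms cannot be graded at all. The documents do not support that, because the general illness row and Section 12.1.3 both apply. The inconsistency remains because both carry the extra Grade 3 condition.

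**Nausea also carries a care condition.** This stands. The contrast is with fatigue, myalgia and headache, not with every other symptom.

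**The diary may solve it.** The diary has its own severity scale (Section 9.1.1), which the documents do not show. It may grade arthralgia and chills as it grades myalgia. The investigator's check against Attachment 1 would then conflict with it. So a reader who infers that these events are in fact under-graded goes beyond the documents.

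**The effect on pausing is limited.** Rule 4 also needs relatedness and 72 hours. Under Section 11.10 the investigator may ask for a review of any single event and may suspend vaccination before a rule is met. Section 1.1 reports that systemic events with the earlier vaccine, at a lower dose, were mostly mild to moderate with a median duration of 1 to 3 days. This stands, and it argues against the higher values of p. It does not make the definitions consistent.

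**Clinical judgment can fill the gap.** The judgment clause in Section 12.1.3 is for events that the subject does not directly experience. Chills and joint pain are directly experienced.

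**Conclusion.** The inconsistency holds on the text. For arthralgia and chills, an event that prevents daily activity without requiring medical intervention cannot be Grade 3, while the same loss of function is Grade 3 for fatigue, myalgia and headache. Grade 3 rates for the two symptoms may be understated relative to those three. Rule 4 may be less sensitive to them for related events lasting 72 hours or longer.

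The size is unknown. The table above shows only how the definition could matter under assumed values of p and q. A reader might infer that the reported rates are biased toward zero, or that the pausing rule fails for these symptoms. The documents support neither, because they give no rates, do not show the diary scale, and contain a Grade 4 wording that could act in the other direction. Safety analysis is descriptive and both arms use the same scale, so the effect is on comparison between symptoms and on rule 4, not on a formal test. The point should be corrected, but it does not threaten the trial's main conclusions.

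**What to change.** Reconcile Section 12.1.3, protocol Attachment 1, the diary scale and the SAP so that arthralgia and chills each have one explicit, named grading entry. The same entry should be used in the diary, in the investigator's verification and in the analysis. The sponsor should choose the criteria and confirm what they mean for pausing rule 4; no threshold is proposed here. In the Grade 3 tables, add a note where symptom definitions differ, including for nausea.

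Point the SAP 7.1.1 fallback to the protocol's clinical grading table, or reproduce that table in the SAP.

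Cost: no new data collection, but the diary must be aligned. Amendment 3 refers to findings from ongoing monitoring, so the trial was already under way. Events already graded may need re-checking, and Grade 3 counts for the two symptoms may change slightly.

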12.2. Special Reporting Situations

Safety events of interest on a sponsor study vaccine that may require expedited reporting and/or safety evaluation include, but are not limited to:

- Suspected abuse/misuse of a sponsor study vaccine
- Accidental or occupational exposure to a sponsor study vaccine
- Medication error involving a sponsor product (with or without subject/patient exposure to the sponsor study vaccine, eg, name confusion)
- Exposure to a sponsor study vaccine from breast-feeding

Special reporting situations should be recorded in the eCRF. Any special reporting situation that meets the criteria of an SAE should be recorded on the serious adverse event page of the eCRF.

12.3. Procedures

12.3.1. All Adverse Events

Unsolicited AEs and special reporting situations will be reported from ICF signature until 28 days after vaccination, and from the entry into the Unit until 28 days after challenge.

From challenge until discharge from the Unit, SSC findings greater than Grade 0 will be presumed to represent virus infection consequent to challenge, and will not additionally be captured as an AE, unless they meet the criteria for an SAE. The changes in RSV viral load will not be reported as AEs or SAEs.

Solicited AEs will be recorded by each subject in the subject diary for 7 days after dosing. The investigator will review each subject's diary at the subsequent in-clinic visit; diary information will be transcribed by the study personnel in the on-site assessment forms in the eCRF.

The sponsor will evaluate any safety information that is spontaneously reported by an investigator beyond the time frame specified in the protocol.

The investigator will monitor and check the study data including all AE and any clinical laboratory data as they become available and will make determinations regarding the severity of the adverse experiences and their relation to study vaccine. All AEs will be deemed related to study vaccine or not related to study vaccine, or related to the viral challenge or not related to viral challenge, according to Section 12.1.2.

The investigator must review both post-injection reactogenicity and other AEs to insure the prompt and complete identification of all events that require expedited reporting as SAEs, invoke pausing rules or are other serious and unexpected events.

All AEs, regardless of seriousness, severity, or presumed relationship to study vaccine, must be recorded using medical terminology in the source document and the eCRF. Whenever possible, diagnoses should be given when signs and symptoms are due to a common etiology (eg, cough,

runny nose, sneezing, sore throat, and head congestion should be reported as “upper respiratory infection”). The investigator must record in the eCRF their opinion concerning the relationship of the AE to study vaccine. All measures required for AE management must be recorded in the source document and reported according to sponsor instructions.

The sponsor assumes responsibility for appropriate reporting of AEs to the regulatory authorities. The sponsor will also report to the investigator (and the head of the investigational institute where required) all SUSARs. The investigator (or sponsor where required) must report SUSARs to the appropriate IEC/IRB that approved the protocol unless otherwise required and documented by the IEC/IRB. A SUSAR will be reported to regulatory authorities unblinded. Participating investigators and IEC/IRB will receive a blinded SUSAR summary, unless otherwise specified.

Each subject will be provided with a “wallet (study) card” and instructed to carry this card with them for the duration of the study indicating the following:

- Study number
- Statement, in the local language(s), that the subject is participating in a clinical study
- Investigator’s name and 24-hour contact telephone number
- Local sponsor’s name and 24-hour contact telephone number (for medical staff only)
- Site number
- Subject number
- Any other information that is required to do an emergency breaking of the blind

12.3.2. Serious Adverse Events

All SAEs occurring from ICF signature until the end of the study must be reported to the appropriate sponsor contact person by study-site personnel within 24 hours of their knowledge of the event.

Information regarding SAEs will be transmitted to the sponsor using the sponsor’s Serious Adverse Event Form, which must be completed and signed by a physician from the study site, and transmitted to the sponsor within 24 hours. The initial and follow-up reports of an SAE should be made by facsimile (fax).

All SAEs that have not resolved by the end of the study, or that have not resolved upon discontinuation of the subject’s participation in the study, must be followed until any of the following occurs:

- The event resolves
- The event stabilizes
- The event returns to baseline, if a baseline value/status is available

- The event can be attributed to agents other than the study vaccine or to factors unrelated to study conduct
- It becomes unlikely that any additional information can be obtained (subject or health care practitioner refusal to provide additional information, lost to follow-up after demonstration of due diligence with follow-up efforts)

Suspected transmission of an infectious agent by a medicinal product will be reported as an SAE. Any event requiring hospitalization (or prolongation of hospitalization) that occurs during the course of a subject's participation in a study must be reported as an SAE, except hospitalizations for the following:

- Hospitalizations not intended to treat an acute illness or an AE (eg, social reasons such as pending placement in long-term care facility)
- Surgery or procedure planned before entry into the study (must be documented in the eCRF). *Note*: Hospitalizations that were planned before the signing of the ICF, and where the underlying condition for which the hospitalization was planned has not worsened, will not be considered as SAEs. Any AE that results in a prolongation of the originally planned hospitalization is to be reported as a new SAE.

The cause of death of a subject in a study during the entire study period, whether or not the event is expected or associated with the study vaccine, is considered an SAE and must be reported.

